Cover page

Official Title: LSA Reconstruction With Laser Fenestration During the TEVAR

NCT number: NCT03845829

Date of the document: November 1, 2020

- **Study Protocol**
- **Objective** This study aimed to prospectively evaluate the safety and efficacy of left subclavian artery (LSA) revascularization via in-situ laser-assisted fenestration during thoracic endovascular aortic repair (TEVAR) for type B aortic dissection (TBAD).
- **Design** This was a prospective, single-arm, multicenter study that enrolled patients with complicated or high-risk acute TBAD. The LLTEVAR (LSA Revascularization With Laser-assisted Fenestration During TEVAR) study is a prospective, single-arm, multicenter trial that planned to enroll 100 patients at 5 vascular centers (NCT03845829). Patients presenting with complicated or high-risk acute TBAD with a proximal entry tear originating in zone 2 or zone 3, who were deemed appropriate candidates for TEVAR in conjunction with LSA revascularization, met the included criteria, and consented to participate were enrolled. The distance from the proximal edge of LSA orifice to the intended proximal landing location should be >5 mm. Patients were excluded if they were pre-procedurally scheduled to have proximal aortic arch coverage in zone 1 or zone 0. Other main exclusion criteria included patients who were inappropriate for TEVAR due to unfavorable anatomic characteristics (no commercially available aortic stent for the size of the aorta, no available access for TEVAR, both LAS and left vertebral artery originated from aorta, et al), previous open surgery for aortic arch and connective tissue disorders. The primary safety endpoint was freedom from composite major adverse events (mortality, stroke, myocardial infarction, rupture, paraplegia, type Ia endoleak) within 30 days after the procedure. Univariate and multivariate analyses determined the risk factors of composite major adverse events. The primary efficacy endpoint was freedom from all-cause death, LSA in-stent restenosis, and reintervention due to dissection progression, growth, and endoleak at 1 year after the procedure.

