- **Statistical Analysis Plan (SAP):** Continuous variables are presented as mean with standard deviation, and categorical variables are summarized using counts and proportion. Univariate logistics regression analysis was performed to determine the potential risk factors of major adverse events (mortality, stroke, myocardial infarction, rupture, paraplegia, type Ia endoleak, major bleeding, acute kidney injury, limb ischemia, bowel ischemia, retrograde dissection, stent-induced new entry (SINE), access site complications and unplanned reinterventions), and only factors being found statistically significant in the univariate analysis were included in the multivariate analysis. The patency rate of LSA and the all cause related mortality were estimated using the Kaplan-Meier method. SPSS version 26.0 (SPSS, Inc., Chicago, IL, USA) was used for the statistical analyses. Differences with a P value < 0.05 were considered statistically significant.
- **Informed Consent Form (ICF):** attachment
-

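### The SAP does not say how deaths enter the Kaplan-Meier curve for LSA patency; if they are censored, the curve gives net patency loss, which slightly exceeds the share of patients who lose patency

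*Combined protocol and SAP*

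**What the plan says.** The Statistical Analysis Plan paragraph contains one sentence on time-to-event methods: "The patency rate of LSA and the all cause related mortality were estimated using the Kaplan-Meier method". It does not define the event that ends patency or the time origin. It does not say whether a death is censored, counted as a failure or treated as a competing event.

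The Design paragraph of the Study Protocol describes a "prospective, single-arm, multicenter trial that planned to enroll 100 patients at 5 vascular centers". It says that the study "enrolled patients with complicated or high-risk acute TBAD". The primary efficacy endpoint there is "freedom from all-cause death, LSA in-stent restenosis, and reintervention due to dissection progression, growth, and endoleak at 1 year after the procedure". Mortality is also a component of the 30-day primary safety endpoint, so the plan itself allows for deaths. No expected patency rate, expected mortality or basis for the sample size is given.

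**The concern.** A patient who dies with an open LSA stent can no longer lose patency. If that death is censored, Kaplan-Meier treats the patient as still able to lose patency later, at the same rate as those who remain under observation. The curve then answers a hypothetical question: what loss would be seen if death did not remove patients? A reader may well take it as the answer to a different one: what share of treated patients lost LSA patency within a year? The two answers differ whenever some patients die first, and they differ more when deaths come early.

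The study's stated objective is the safety and efficacy of LSA revascularization by laser fenestration, so patency is the result most specific to the technique. Readers will probably quote it as an absolute risk. The SAP should say which quantity it is.

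**Working it through.** **Inputs.** From the documents: N = 100 (Design), Kaplan-Meier for LSA patency with mortality estimated separately (SAP), and a 1-year horizon (primary efficacy endpoint). The plan states no patency or mortality figure, so there is nothing of its own to reproduce. Assumed here: net 1-year patency loss F of 5% or 10%, and 1-year mortality D of 5%, 10% or 15%.

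**Direction.** Both estimators add up the same event rates over time. Kaplan-Meier with deaths censored weights each by the probability of not yet having lost patency. Aalen-Johansen weights each by the probability of being alive with patency intact. The second weight is never larger than the first, so 1 minus Kaplan-Meier is never below the cumulative incidence. This holds whether or not death and stent failure are related.

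**A small example.** Take 100 patients, with 10 deaths followed by 5 losses of patency and no other censoring. Kaplan-Meier gives 1 − 85/90 = 5.56%. The cumulative incidence is 5/100 = 5.00%. With 5 early deaths instead, the figures are 5/95 = 5.26% and 5.00%.

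**Constant, independent hazards.** Let a = −ln(1 − F) and b = −ln(1 − D). Then 1 minus Kaplan-Meier at 1 year equals F, and the cumulative incidence is a/(a + b) × [1 − exp(−(a + b))]. For F = D = 10%, a = b = 0.1054, so the cumulative incidence is 0.5 × (1 − 0.81) = 9.50%, a gap of 0.50 points.

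**All deaths at day 30.** The cumulative incidence is [1 − exp(−30a/365)] + (1 − D) × [exp(−30a/365) − (1 − F)]. For F = 10%, exp(−30a/365) = 0.9914. At D = 15% this gives 0.0086 + 0.85 × 0.0914 = 8.63%, a gap of 1.37 points.

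| Net loss F (1 − KM) | Mortality D | Cumulative incidence, constant hazards | Gap (points) | Cumulative incidence, deaths at day 30 | Gap (points) |
|---|---|---|---|---|---|
| 5% | 5% | 4.88% | 0.12 | 4.77% | 0.23 |
| 5% | 10% | 4.75% | 0.25 | 4.54% | 0.46 |
| 5% | 15% | 4.62% | 0.38 | 4.31% | 0.69 |
| 10% | 5% | 9.75% | 0.25 | 9.54% | 0.46 |
| 10% | 10% | 9.50% | 0.50 | 9.09% | 0.91 |
| 10% | 15% | 9.24% | 0.76 | 8.63% | 1.37 |

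A simulation of 2 million patients at F = 5%, D = 10% with constant hazards gave 5.03% against 4.77%, in line with the formula.

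**Against sampling error.** The approximate standard error is √[F(1 − F)/100]: 2.2 points at 5% and 3.0 points at 10%. The largest gaps are 0.69/2.18 = 0.32 and 1.37/3.0 = 0.46 of a standard error.

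**More extreme rates.** At F = D = 20% the gap is 2.0 points with constant hazards. If every death came at the very start it would be F × D = 4.0 points, against a standard error of 4.0.

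**The case against.** The strongest reply is that Kaplan-Meier is not wrong here; it estimates something else. In the calculation above it returns exactly the net loss that was put in. For a question about stent durability, net patency is a reasonable target. Cumulative incidence has a drawback of its own: with the same stent, loss falls from 9.75% to 9.24% merely because mortality rises from 5% to 15%. This reply stands. It means that Kaplan-Meier cannot be called simply biased, and that the net curve is worth keeping. It does not settle the matter, because the SAP does not say that net patency is the target, and the estimate relies on death being independent of stent failure, which the SAP does not state either.

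Four stronger readings are tempting, and the documents do not support them:

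- *That the SAP censors deaths.* It has no censoring rule. If deaths were counted as failures, the curve would be patency-free survival and this problem would not arise.
- *That the direction of error is known in every sense.* It is known relative to cumulative incidence. If death and stent failure are related, the direction of error for net patency is not known. For example, if patients likely to die are also likely to lose patency, Kaplan-Meier understates net loss.
- *That the primary efficacy result is distorted.* Death is a component of that composite, so it does not compete with it.
- *That the two curves were meant to be combined into the composite.* The SAP does not propose this. It names no estimator for the composite, which is a separate matter that a change to the patency analysis would not resolve.

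It is also fair to say that the plan states no patency threshold or comparator, so no decision shown in the documents depends on a gap of this size.

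**Conclusion.** The point holds as a minor one. The SAP leaves the handling of deaths in the patency curve unstated. On the natural reading, 1 minus Kaplan-Meier is a net figure that exceeds the actual proportion of treated patients who lose LSA patency.

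The excess is about 0.1 to 1.4 points, under half of one standard error with 100 patients. It overstates loss, so it is conservative for the technique and unlikely to change the study's conclusion. Unlike sampling error, however, it runs in one direction and would not shrink with more patients.

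This rests on two things the documents do not give: that deaths are censored, and the assumed rates of 5-10% loss and 5-15% mortality. The top of the range needs 15% mortality with every death at day 30. The direction relative to cumulative incidence needs only the first.

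**What to change.** In the SAP, name the event that counts as loss of LSA patency and its time origin, and state that death before that event is a competing event. Report the 1-year cumulative incidence of patency loss by the Aalen-Johansen estimator, with a 95% confidence interval, as the absolute risk. Keep the Kaplan-Meier patency curve alongside, labelled as net patency with deaths censored, for comparison with other series. Kaplan-Meier remains right for all-cause mortality.

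The cost is one or two SAP sentences and a short extra analysis, possibly outside SPSS, the only package the SAP names. No new data are needed beyond the dates of patency loss, death and last follow-up that the planned curves already require.
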